## 8 Study Objectives

1. To assess tumor heterogeneity by analyzing longitudinal tumor samples.
2. To define biomarkers to predict resistance to systemic therapy, in the neoadjuvant, adjuvant and metastatic setting.
3. To describe the change in breast cancer subtype and in molecular markers after systemic therapy.
4. To identify new prognostic biomarkers associated with worse long-term outcome (e. g. disease-free, progression-free survival and overall survival).
5. To identify possible markers predictive for tumor sensitivity for post-neoadjuvant and palliative systemic therapies.
6. To identify new druggable targets which could be investigated for post-neoadjuvant and palliative treatment.

## 9 Study Design

MOMENTUM is a prospective registry trial with a non-interventional translational design. The goal of the trial is to obtain longitudinal biomaterial pairs (at least two tumor samples) representing different clinical situations, to assess molecular changes during disease progression. Eligible early breast cancer patients should preferably be enrolled in the study prior to surgery (after NACT) to allow for collection of fresh tumor tissue in addition to formalin-fixed paraffin embedded (FFPE) breast tumor tissue. Patients might also be enrolled after surgery to provide FFPE tumor tissue only. Patients with metastatic breast cancer may be enrolled only if they have received oncologic treatment and have experienced tumor progression during/after this therapy irrespective of the clinical situation in which therapy was applied (neoadjuvant/adjuvant or metastatic setting). Clinical information on oncologic/medical history are collected at baseline, and follow up information on subsequent cancer therapies and oncologic outcomes will be collected. To analyze association of molecular parameters with the clinical outcome, only tissues will be collected that were obtained during routine procedures. Archived samples from the primary tumor (untreated and/or after NACT) will be collected to assess molecular changes during tumor progression via longitudinal comparisons.

## 10 Study Population

### 10.1 Inclusion Criteria

1. Patients with eBC and clinically gross residual tumor after NACT or distant recurrence of breast cancer during/after (neo-)adjuvant therapy or mBC with progression after at least one line of therapy for mBC.
2. All patients must be able to provide a pair of longitudinal tissue samples namely:
  - one breast tumor sample before NACT and one after NACT for patients with eBC
  - one sample before (breast tumor or metastasis) and one sample after (metastasis) disease progression occurred for patients with mBC.
3. Female and male breast cancer patients aged  $\geq 18$ .
4. Participation is allowed independently of breast cancer histology (ductal, lobular, others) and of breast cancer subtype (Luminal A, luminal B, HER2-positive, triple-negative).
5. Informed consent for data collection and biomaterial collection.
6. Participation in other interventional clinical trials is allowed.

### 10.2 Exclusion Criteria

1. Patients with a history of any malignancy beside breast cancer are ineligible with the following exceptions:
  - a. Disease-free for at least 5 years (last assessment must have been performed within 3 months before inclusion) and the features of the primary tumor are considered low risk.
  - b. CIS of the cervix, basal cell and squamous cell carcinomas of the skin.
2. Patients with no histological verification of the diagnosis of breast cancer.
3. Patients with eBC or de novo mBC that have not received any systemic therapy.
4. Tissue acquirement either by biopsy or during surgery not possible.
5. Any physical or mental condition or severe comorbidities that would compromise the adequate cooperation of the patient.
6. History of significant neurological or psychiatric disorders that would prohibit the understanding of the study purpose and giving of informed consent.

## 11 Collection of Biomaterials

### 11.3 Patient recruitment and consenting

[figure not shown]
Patients will be screened for eligibility during interdisciplinary oncologic conferences (preoperative or metastatic) at the participating sites. During consulting with the treating physician/investigator the purpose of the study, obligations, risks and potential benefits will be discussed with the patient. After a check for compliance with the inclusion/exclusion criteria, written informed consent will be obtained. Details for informed consenting are described in part 16.4.

The retrospective inclusion of deceased patients with secondary mBC and distant progression after initial neoadjuvant and/or adjuvant therapy and archived residual biomaterial and clinical data is possible in accordance with the "Empfehlung für die Bewertung forschungsbezogener Biobanken durch Ethik-Kommissionen empfohlen vom Arbeitskreis Medizinischer Ethik-Kommissionen Version 2.1. gemäß Beschluss vom 24.6.2022".

[figure not shown]
The use shall be restricted to breast cancer research. The identification of molecular markers for drug resistance has the power to protect patients from ineffective but side-effect-prone therapies, to identify potentially superior therapies and to optimize the allocation of resources in the healthcare system. Hence the scientific interest in identifying these mechanisms represents an enormous value that serves the common good of health care research, the interests of individual patients as well as the population and society as a whole.

**11.1 Overview**

**11.1.1 eBC patients with clinically gross residual tumor after neoadjuvant chemotherapy**

[figure not shown]

**11.1.2 Enrollment of patients with secondary mBC and distant progression after initial neoadjuvant and/or adjuvant therapy**

### 11.1.3 Enrollment of patients with de-novo mBC and progression after at least 1 line of metastatic therapy

## 11.2 Tumor Tissue

### Early breast cancer:

- FFPE breast tumor tissue must be collected from primary tumor, before NACT and at surgery after NACT. If recurrence occurs, FFPE from metastasis will be collected, whenever feasible. If no biopsy of first recurrence is possible/available, then also material from later recurrences may be collected.
- Optional collection: Fresh tumor tissue from the residual tumor should be collected at surgery. The collected tissue needs to be shock frozen in liquid nitrogen and then stored at -80°C or in liquid nitrogen. GBG will organize transportation of the fresh frozen tissues to the GBG biobank.
- To note: Tissue of lymph nodes may be sent additionally to breast tumor tissue, if available

### Metastatic breast cancer:

- After neoadjuvant therapy: FFPE from metastasis must be collected; additionally, FFPE from core biopsy of the primary breast tumor prior to NACT and/or surgical tissue in case of

residual tumor after NACT will be collected. FFPE from metastasis of following biopsies during disease progression will be collected whenever feasible.

- After adjuvant therapy: FFPE from metastasis must be collected; additionally, FFPE from primary breast tumor (core biopsy or surgical tissue) will be collected. FFPE from metastasis of following biopsies during disease progression will be collected whenever feasible.
- In de novo mBC FFPE from metastasis and or breast tumor prior to any therapy and after progression after at least one line of systemic treatment must be collected. FFPE from metastasis of following biopsies during disease progression will be collected whenever feasible.
- To note: Tissue of lymph nodes may be sent additionally to breast tumor tissue, if available.

### **11.3 Blood**

- 10 mL EDTA blood will be collected after enrollment.
- 20 mL EDTA blood will be collected after enrollment, and at the beginning of subsequent therapy lines (if oncologic treatment was changed due to disease progression) for plasma preparation and subsequent analysis of circulating tumor DNA (ctDNA). Especially in case of biopsy of metastasis during treatment progression a timely EDTA blood sample should be collected.

### **11.4 Storage and Logistics of Biomaterial**

- FFPE tissue will be sent to the GBG Biobank at Marburg ([name], Institute of Pathology, UKGM Marburg).
- Fresh Frozen Tissue will be stored at -80°C at the site, until shipment is organized by GBG.
- EDTA blood and plasma will be stored at -20°C/-80°C at the site, until shipment is organized by GBG.

## **12 Discontinuation patient, site or study**

### **12.1 Treatment Discontinuation of Individual Patient**

If a patient shows one of the following reasons the study participation must be discontinued:

- Patient's death
- Patient's request or non-compliance.

The reason and date of discontinuation for all patients will be documented on the eCRF (e.g. death, withdrawal of consent, lost to follow-up, etc.).

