	
positive, triple-negative) but will focus on high-risk tumors such as TNBC and luminal B.
 
5. Informed consent for data collection and biomaterial collection.
 
6. Participation in other interventional clinical trials is allowed.

Exclusion Criteria	
 
1. Patients with a history of any malignancy beside breast cancer are ineligible with the following exceptions: 
 
a. Disease-free for at least 5 years (last assessment must have been performed within 3 months before inclusion) and the features of the primary tumor are considered low risk.
 
b. CIS of the cervix, basal cell and squamous cell carcinomas of the skin.
 
 
 
2. Patients with no histological verification of the diagnosis of breast cancer.
 
3. Patients with eBC or de novo mBC that have not received any systemic therapy.
 
4. Tissue acquirement either by biopsy or during surgery not possible.
 
5. Any physical or mental condition or severe comorbidities that would compromise the adequate cooperation of the patient.
 
6. History of significant neurological or psychiatric disorders that would prohibit the understanding of the study purpose and giving of informed consent.
 

Study Procedures and Examinations	
MOMENTUM is a non-interventional registry trial with a focus on real world patients. Clinical information on oncologic/medical history are collected at baseline, and follow up information on subsequent cancer therapies and oncologic outcome will be collected. To analyze association of molecular parameters with the clinical outcome, only tissues will be collected that were obtained during routine procedures (e. g. diagnostic core biopsy, surgery, etc.). The blood collection for whole blood and plasma sampling should be scheduled during routine visits. No study-specific interventional procedures or examinations are planned. The retrospective inclusion of deceased patients with secondary mBC and distant progression after initial neoadjuvant and/or adjuvant therapy and archived residual biomaterial and clinical data is possible in accordance with the "Empfehlung für die Bewertung forschungsbezogener Biobanken durch Ethik-Kommissionen empfohlen vom Arbeitskreis Medizinischer Ethik-Kommissionen Version 2.1. gemäß Beschluss vom 24.6.2022"

Patients	Approx.2000
FU	Patients will be followed-up for 5 years.
Sites	Ca. 50

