### **15 Follow up**

Data will be collected within the MOMENTUM study during recruitment phase. After LPI the data collection will be continued for all included patients for 5 years.

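### Section 12.1 makes undefined non-compliance a mandatory reason to end participation, which conflicts with Section 15 and can cause avoidable informative censoring of survival outcomes.

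*Protocol*

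**What the plan says.** Section 12.1 sets a mandatory rule: "If a patient shows one of the following reasons the study participation must be discontinued". Two bullets follow. One is the patient's death, the other reads "Patient's request or non-compliance". Non-compliance is not defined. On what happens next, the section says only "The reason and date of discontinuation for all patients will be documented on the eCRF". It does not separate stopping sample collection from stopping outcome data.

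The Synopsis describes a registry in which little can be complied with: "No study-specific interventional procedures or examinations are planned". Tissue comes from routine procedures or archives. Blood is taken at routine visits: "20 mL EDTA blood will be collected after enrollment, and at the beginning of subsequent therapy lines" (Section 11.3).

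On follow-up, the Synopsis says "Patients will be followed-up for 5 years", and Section 15 says "After LPI the data collection will be continued for all included patients for 5 years". Neither makes an exception for a discontinued patient. The outcomes concerned belong to objective 4 in Section 8: "To identify new prognostic biomarkers associated with worse long-term outcome (e. g. disease-free, progression-free survival and overall survival". Section 14.6 lists survival among the data to be collected.

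**The concern.** A rule that ends participation for non-compliance has a purpose in a trial with an assigned treatment. Here it has no evident purpose. A patient who wishes to leave is already covered by the patient's request in 12.1 and by the right to withdraw in Section 16.4.

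The rule can do harm in one way. Suppose a site closes the record of a patient who misses samples or visits, and such patients have a worse prognosis than those who stay. Kaplan-Meier and Cox estimates assume that censored patients have the same future hazard as those still at risk. That assumption would fail, and survival would look too long. An analysis plan cannot restore outcome data that were never collected, so the matter has to be settled in the protocol.

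**Working it through.** **Text check.** Take one living patient who is judged non-compliant and has not withdrawn consent.

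- Under 12.1, participation must end. Only the reason and date are required.
- Under Section 15, data collection continues for 5 years after LPI, because the patient is an included patient.

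On the ordinary meaning of ended participation, a site cannot follow both. About 50 sites (Synopsis) would each have to choose, without a definition of non-compliance.

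**Size.** The protocol has no dropout, event or power figure to reproduce. Every rate below is an assumption.

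Inputs:
- S, 5-year survival without removal: 30% or 70%.
- q, share of patients assigned a removal time, uniform over 0 to 5 years: 5%, 10% or 20%. Some die before that time, so fewer are actually removed (at q = 10%, 5.8% when S = 30% and 8.4% when S = 70%).
- h, hazard ratio after removal relative to before: 1 to 3.

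Formula, with exponential survival, L = -ln S and a = (h - 1)L:
- Kaplan-Meier with censoring at removal estimates S.
- True survival is (1 - q)S + qS(1 - e^-a)/a.
- Overestimate = qS[1 - (1 - e^-a)/a]. It tends to 0 as h approaches 1.

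Worked case, S = 0.70, q = 0.20, h = 3: L = 0.3567 and a = 0.7133. Then (1 - e^-a)/a = 0.51/0.7133 = 0.7149. The overestimate is 0.20 x 0.70 x 0.2851 = 0.040, or 4.0 points.

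Overestimate of 5-year survival, in percentage points:

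| q | h = 1 | h = 1.5, S = 30% / 70% | h = 2, S = 30% / 70% | h = 3, S = 30% / 70% |
|---|---|---|---|---|
| 5% | 0 | 0.4 / 0.3 | 0.6 / 0.6 | 0.9 / 1.0 |
| 10% | 0 | 0.7 / 0.6 | 1.3 / 1.1 | 1.9 / 2.0 |
| 20% | 0 | 1.5 / 1.2 | 2.5 / 2.2 | 3.7 / 4.0 |

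A simulation of 400,000 patients per scenario agrees to within 0.1 point. Between 2% and 20% of events were lost.

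**Near-worst case.** Assume instead that a share x of the deaths within 5 years is replaced by censoring 1 to 6 months earlier, and that no survivor is removed. The observed hazard falls to about (1 - x) of the true one, so the estimate is about S^(1 - x).

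- Median 36 months: S = 0.5^(60/36) = 31%. Simulation gives 33%, 35% and 39% for x = 5%, 10% and 20%. At x = 10% the median becomes 36/0.9 = 40 months.
- Median 48 months: S = 0.5^(60/48) = 42%. Simulation gives 44%, 46% and 50%.

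**Marker hazard ratio.** The marker hazard ratio was set to 1.5 before removal, and 5-year survival to 60% in marker-negative patients.

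- Equal removal, 10% in each group: full follow-up 1.49 to 1.50, observed 1.49 to 1.51. There is practically no change.
- Unequal removal, 5% versus 20% or 10% versus 30% with more in marker-positive patients, and h = 2 or 3: full follow-up 1.57 to 1.68, observed 1.49 to 1.51. The association is attenuated.

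**The case against.** The strongest objection is that 12.1 ends participation and nowhere says that survival follow-up stops, whereas Section 15 keeps every included patient. A reader might infer that 12.1 does end survival follow-up. The text does not establish that. It establishes a contradiction, and the censoring follows only if sites let 12.1 prevail.

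A reader might also infer that a single missed tube triggers removal. Nothing says so. Non-compliance shares a bullet with the patient's request, and the examples of recorded reasons are death, consent withdrawal and loss to follow-up. Later metastasis samples are taken only where feasible, so a missing block is hardly the patient's non-compliance.

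A third inference is that the rule biases PFS and OS. The documents give no non-compliance rate and no link to prognosis, so only the possibility is supported. No effect on PFS has been shown: blood after enrollment is due when a new line starts after progression, so a tube missed then comes after that progression, not before it.

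It is also true that a patient who stops attending may leave no routine record at the site. That loss would occur without the rule. Finally, Section 13 describes an exploratory, descriptive analysis, and the near-worst case assumes that only patients about to die are removed.

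These points limit the size and certainty of the harm. They do not remove the conflict between 12.1 and 15, and they give no reason to keep the rule. Descriptive survival estimates and marker associations also depend on uninformative censoring.

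**Conclusion.** The point holds as a contradiction in the protocol with a possible, unquantified effect on survival outcomes. Section 12.1 compels discontinuation for an undefined reason, and Section 15 requires data on the same patient.

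Bias needs two conditions that the documents do not settle: sites treat 12.1 as ending follow-up, and non-compliance is related to prognosis. If both hold, the overestimate of 5-year survival is about 0.6 to 2 points with 10% of patients assigned to removal, and at most about 4 points with 20%, for a hazard ratio after removal of 1.5 to 3. If removal is unrelated to prognosis, it is 0. Figures such as 31% rising to 35% arise only when removals are concentrated in the months before death. Marker hazard ratios are attenuated only if removal differs by marker group.

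No confirmatory endpoint is affected. The change is still worth making, because it removes an avoidable risk at almost no cost.

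**What to change.** In Section 12.1, delete non-compliance as a reason for discontinuing participation. Add that a missed sample or visit ends at most sample collection. Therapy, progression and survival data continue to be recorded from available routine records until death, study close-out, loss to follow-up or withdrawal of consent. Section 12.1 then agrees with Section 15, and the bias due to this rule is zero in every scenario above. Ordinary loss to follow-up remains.

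The cost is one deleted phrase and a short added statement in an amendment, with no extra visits. Patients who want to leave keep that right.

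Retitling 12.1, whose heading refers to treatment although the registry gives none, is editorial only. The handling of data after consent is withdrawn may be covered in the consent pages, which are not available here, so nothing is claimed about it.

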### **12.2 Premature Termination of Study at a Particular Site**

The GBG Forschungs GmbH as the sponsor has the right to close this study at a particular study site which may be due to but not limited to the following reasons:

- Non-compliance with the protocol
- Insufficient number of recruited patients
- Inadequate co-operation with GBG Forschungs GmbH or its representatives
- The Investigator requests to close of his/her study site
- Quality issues

### **12.3 Premature Termination of the study**

The GBG Forschungs GmbH as the sponsor has the right to close this study, e.g., if the study conduct (e.g., recruitment rate; drop-out rate; data quality; protocol compliance) does not suggest a proper completion of the study within a reasonable time frame.

## **13 Statistics**

This explorative and descriptive approach will generate novel hypotheses. The analyses will generate heterogeneous individual molecular datasets, which do not allow planning of classical statistical procedures. Hence, this explorative trial will not use a fixed framework of statistical assumptions, which determines sample size and power since there will be also no specific treatment arms at the beginning. Analysis will be descriptively.

## **14 Data Management**

### **14.1 Data Management and Documentation**

Data management will be carried out by the GBG Forschungs GmbH using a web-based EDC (Electronic Data Capture) system that is FDA 21 CFR Part 11 compliant. Data management activities include CRF design, database creation, data processing and data validation.

### **14.2 Data Entry and Queries**

All CRF data will be entered into the trial database using a web-based EDC system, which will perform automated plausibility and value range checks before accepting the data into the database. CRF data will be reviewed; data fields that do not match the trial guidelines will be queried. These queries are forwarded to the center for resolution. The data will be checked by a data manager and either closed or re-queried.

### **14.3 Data Validation**

Visual and computerized methods of data validation are applied in order to ensure accurate, consistent and reliable data.

### **14.4 Pseudonymization**

In order to protect patient data confidentiality and for safeguarding the privileged doctor patient relationship, each participating patient is assigned a unique GBG reference number. Instead of the true patient identity the pseudonym is used in all communication between the trial site and the GBG

Forschungs GmbH. Each patient will receive a study subject ID, for which a subject log needs to be stored at the site.

#### **14.5 User Access Control**

Every user is provided with a unique personal username and unique password which defines their access rights as well. Access control is based on the User Role in the web-based EDC system. Therefore, users can only access and amend those datasets necessary for them to fulfil their tasks.

#### **14.6 Data Collection**

The following data will be collected:

- Baseline demographic and tumor characteristics
- Neoadjuvant Chemotherapy
- Surgery
- Post-neoadjuvant therapy
- Adjuvant therapy
- Clinical follow up on oncologic medications for treatment of metastasis and survival
- Biomaterial data (biopsies, blood samples)

### **15 Follow up**

Data will be collected within the MOMENTUM study during recruitment phase. After LPI the data collection will be continued for all included patients for 5 years.

### **16 Legal and Ethical Considerations**

#### **16.1 Declaration of Helsinki**

This study is to be performed in accordance with the Declaration of Helsinki (Fortaleza, October 2013).

#### **16.2 Beratung nach §15 Berufsordnung der Bundesärztekammer**

The study will be assessed by the Ethik-Kommission der Landesärztekammer Hessen, [name]. The study will only be started after being approved by the ethics committee.

#### **16.3 Funding**

The funding will be guaranteed by the GBG Forschungs GmbH. Additionally, the study will be supported by funding from Deutsche Krebshilfe (INTEGRATE-TN) and BMBF (SATURN3).

#### **16.4 Patient Informed Consent and Patient Insurance**

Prior to enrollment and tissue/blood sample collection according to protocol, the patient is informed about the intended purpose, possible benefits, and possible adverse experiences.

An approved informed consent (ICF) statement will then be read and signed by the patient, and, if required, a witness, as well as the investigator. The patient will be provided with a copy of the signed ICF. The patient may withdraw from the study at any time in any way without prejudicing future medical treatment.

Patients are informed that pseudonymized data from their case may be stored electronically and that such data will not be revealed to any unauthorized third party. Data will be reviewed by the monitor, an independent auditor and possibly by representatives of regulatory authorities and/or ethics committees. The terms of the local data protection legislation will be applied as appropriate.

A patient insurance for the compensation of patients for possible study-related injury is not required as no study specific interventions are planned. Only biomaterial, which is collected during standard of care procedures, will be acquired and used for study specific analyses.

